7.9.1.3.2 Mean of Sensor glucose Values and GMI

Mean number of sensor glucose (SG) in mg/dL and GMI will be analyzed and reported. The mean SG and GMI for a subject at period *j* will be calculated as the overall mean of the SG and GMI values (maximum of 8064 readings closer to the visit during the period).

7.9.1.3.3 Standard Deviation (SD) and Coefficient of Variation of Sensor Glucose Values (CV)

The standard deviation (SD) and coefficient of variation of sensor glucose values (CV) will be analyzed and reported. The CV for subject *i* at period *j* will be calculated as:

$$\frac{\text{standard deviation of sensor glucose values for subject } i \text{ at period } j}{\text{mean of sensor glucose values for subject } i \text{ at period } j}$$

The mean of sensor glucose values for subject *i* at period *j* will be calculated as described in section 7.9.1.2.3. The standard deviation of sensor glucose values for subject *i* at period *j* will be the standard deviation of all sensor readings (with maximum of 4032 recent readings) during period *j*.

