13.7. Handling Missing Data

Primary endpoints and Secondary endpoints will be collected at baseline, end of 3 months and end of 6 months and primary and secondary analysis will be based on ITT (Intention to Treat).

For the primary analysis (change of A1c), if A1c at 3 months or 6 months is not available in subjects that drop-out of the study, various sensitivity analyses will be performed:

- Per Protocol Dataset
- Baseline Observation Carry Forward (BOCF)
- Data will be imputed by selected A1c data from the same arm considering baseline characteristics such as age, gender and duration of diabetes

For the secondary endpoints, as suggested by International Consensus Group (ICG), during the two weeks period of SG comparison at 3 months and 6 months between control and treatment arm, a minimum number of 2880 of SG values (288 SG values/day \times 10 days out of 14 days) is required to evaluate the glycemic outcome. For those subjects with less than 2880 SG during the two weeks of sensor wear, the following sensitivity analysis will be carried out to mitigate the impact of data loss:

- CGM data gap filled within the same subject: Missing CGM data in one arm will be imputed by randomly replaced CGM data in the same subject during the same period of sensor wear.
- CGM data gap filled within the arm, ignoring baseline characteristics: Missing CGM data will be imputed by a randomly selected CGM data from the same arm, ignoring baseline characters during the same period of sensor wear.
- CGM data gap filled within the arm, considering baseline characteristics: Missing CGM data will be imputed by selected CGM data from the same arm, considering baseline characters such as age, gender and duration of diabetes during the same period of sensor wear.

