7.9.1.2 Secondary Endpoints

The blinded (for study period) or unblinded (for continuation phase) sensor data collected during the 2 periods of 2 weeks (at 3 months and 6 months for the study phase, and at 9 month and 12 month in the continuation phase) will be combined and then used to perform all statistical test mentioned below. Descriptive summaries of all outcomes mentioned below generated with all 6 month SG data in continuation phase will be provided as well.

7.9.1.2.1 Percentage of Time in Range (70-180 mg/dL), in Hyperglycemia (> 180 mg/dL, > 250 mg/dL) and Hypoglycemia (< 54 mg/dL, < 70 mg/dL)

Percentage of time spent within range with sensor glucose (SG) between 70 - 180 mg/dL (3.9-10.0 mmol/L), in hyperglycemic range with SG > 180 mg/dL (> 10.0 mmol/L), > 250 mg/dL (13.9 mmol/L) and in hypoglycemic range with SG < 54 mg/dL (3.0 mmol/L), < 70 mg/dL (3.9 mmol/L) will be computed using the sensor data collected during each of the 2 periods of 2 weeks. The last 8064 sensor readings (4 weeks) from each period will be used for analysis.

The percentage of time spent within range (70-180 mg/dL) for subject i at period j will be calculated as:

$$\frac{\text{Total number of sensor reading with SG between } 70 - 180 \text{ mg/dL for subject i at period j}}{\text{Total number of sensor readings for subject i at period j}}$$

The percentage of time spent in hyperglycemic range > 180 mg/dL or > 250 mg/dL for subject i at period j will be calculated as:

$$\frac{\text{Total number of sensor reading with SG } > 180 \text{ or } > 250 \text{ mg/dL for subject i at period j}}{\text{Total number of sensor readings for subject i at period j}}$$

Similarly, the percentage of time spent in hypoglycemic range < 54 mg/dL or < 70 mg/dL for subject i at period j will be calculated as:

$$\frac{\text{Total number of sensor reading with SG } < 54 \text{ or } < 70 \text{ mg/dL for subject i at period j}}{\text{Total number of sensor readings for subject i at period j}}$$

The within group difference of Time in specific range (70-180, <54, <70, >180, >250 mg/dL) between study period and continuation phase will be compared using paired t test if normality assumption is met, Wilcoxon signed rank test if normality assumption is rejected.

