7.9.1.3 Ancillary Endpoints

The blinded (for study period) or unblinded (for continuation phase) sensor data collected during the 2 periods of 2 weeks (at 3 months and 6 months for the study phase, and at 9 month and 12 month in the continuation phase) will be combined and then used to perform all statistical test mentioned below. Descriptive summaries of all outcomes mentioned below generated with all 6 month SG data in continuation phase will be provided as well.

Superiority test will be applied to ancillary endpoints if needed.

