7.9.1.3.1 Number of Biochemical Hypoglycemic events

A biochemical hypoglycemic event with SG < 54 mg/dL is defined as sensor glucose values less than 54 mg/dL (3.0 mmol/L) for 15 or more consecutive minutes. A biochemical hypoglycemic event with SG < 70 mg/dL is defined as sensor glucose values less than 70 mg/dL (3.9 mmol/L) for more than 20 consecutive minutes. When the time between two successive events is less than 30 minutes, they will be combined and counted as one event. The mean number of biochemical hypoglycemic events with SG < 54 mg/dL (3.0 mmol/L), < 70 mg/dL (3.9 mmol/L) per subject per week based on 15 and 20 consecutive minutes will be computed using the sensor data collected during each of the 2 periods of 2 weeks. The last 4032 sensor readings (2 weeks) from each period will be used for analysis. The mean number of hypoglycemic events (MNHE) per week at each period for each subject will be calculated as:

$$\frac{\text{number of biochemical hypoglycemic event for subject } i \text{ at period } j}{\text{duration of sensor wear for subject } i \text{ at period } j \text{ in weeks}}$$

Where the duration of sensor wear for subject *i* at period *j* is the number of sensor readings (capped at 4032) for subject *i* at period *j* divided by 2016. Mean number of biochemical hypoglycemic events with SG < 54 mg/dL (3.0 mmol/L) based on 20 minutes definition and < 70 mg/dL (3.9 mmol/L) per week based on 15 minutes definition will be analyzed and reported as additional analyses. Analysis on mean number of biochemical hypoglycemic events with SG < 54 mg/dL (3.0 mmol/L) (based on 15 minutes) will be using non-inferiority test with non-inferiority margin of 35% of the observed mean in the control group.

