7.9.2.3.3 Standard Deviation (SD) and Coefficient of Variation of Sensor Glucose Values (CV)

The standard deviation (SD) and coefficient of variation of sensor glucose values (CV) will be analyzed and reported. The CV for subject i at period j will be calculated as:

$$\frac{\text{standard deviation of sensor glucose values for subject i at period j}}{\text{mean of sensor glucose values for subject i at period j}}$$

The mean of sensor glucose values for subject i at period j will be calculated as described in section 7.9.1.2.3. The standard deviation of sensor glucose values for subject i at period j will be the standard deviation of all sensor readings during period j.

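### In the control group, the SAP caps the SD in the coefficient of variation at 4032 readings but leaves the mean to a section that does not exist; the only definition of that mean allows 8064

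*SAP*

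**What the plan says.** SAP 7.9.1.3.3 covers the control group. It gives the CV for subject i at period j as the SD of sensor glucose divided by its mean.

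- **Numerator.** The SD is "the standard deviation of all sensor readings (with maximum of 4032 recent readings" during the period.
- **Denominator.** The mean "will be calculated as described in section 7.9.1.2.3". The SAP has no such section; under 7.9.1.2 there is only 7.9.1.2.1.
- **Nearest definition of the mean.** SAP 7.9.1.3.2, directly above, defines mean sensor glucose for the control group with a "maximum of 8064 readings closer to the visit during the period".

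The surrounding text sets the data window. The lead-in to SAP 7.9.1.3 says that the two 2-week windows of each phase (3 and 6 months; 9 and 12 months) "will be combined and then used to perform all statistical test mentioned below". SAP 7.9.1.3.4 computes MAGE, the neighbouring variability measure, on 4 weeks per phase.

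For the treatment group, SAP 7.9.2.3.3 puts no cap on the SD: it "will be the standard deviation of all sensor readings during period j". It repeats the same dead reference for the mean.

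**The concern.** A CV describes spread relative to level in one set of readings. If the SD comes from the most recent 2 weeks and the mean from 4 weeks, the ratio mixes two sets and can lie below or above the CV of either. The SD reported in the same section has the same problem, because it is a 2-week figure shown beside a 4-week mean.

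CV is listed as an ancillary endpoint in Protocol 5.3.3, and SAP 7.2 plans paired comparisons of study phase with continuation phase for ancillary endpoints. The distortion in each phase depends on how glucose moved between that phase's two windows, so it need not cancel in the comparison. SAP section 8 requires only code review, as a minimum, for outputs other than the primary and secondary endpoints, and a code reviewer would have no valid section against which to check the mean.

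**Working it through.** **Step 1: what the caps mean.** Protocol 13.7 gives "288 SG values/day".

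- 288 × 14 days = 4032. SAP 7.9.1.3.1 agrees: "The last 4032 sensor readings (2 weeks) from each period will be used for analysis".
- 288 × 28 days = 8064. SAP 7.9.1.2 agrees: "The last 8064 sensor readings (4 weeks) from each period will be used for analysis".

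Both stated durations are reproduced exactly. At full wear the SD covers half the span of the mean.

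**Step 2: formulas.** Let the earlier window have mean m1 and SD s1, and the recent window m2 and s2, with 4032 readings each.

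- Combined mean M = (m1 + m2)/2
- Combined variance S² = (s1² + s2²)/2 + (m1 − m2)²/4
- CV as written = s2/M
- 4-week CV = S/M
- 2-week CV = s2/m2

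Against the 4-week CV the denominator is the same, so the relative error is s2/S − 1. It depends on the SDs as well as on the means.

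**Step 3: one example in full.** The documents give no glucose values, so these are assumed: m1 = 200, m2 = 180, s2 = 60 mg/dL. Then M = 190.

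- As written: 60/190 = 31.6%.
- 4-week CV with s1 = 60: S² = 3600 + 100 = 3700, S = 60.8, and 60.8/190 = 32.0%. Relative error 60/60.8 − 1, about −1.4%.
- 4-week CV with s1 = 70: S² = 4250 + 100 = 4350, S = 66.0, and 66.0/190 = 34.7%. Relative error 60/66.0 − 1, about −9%.

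**Step 4: range under other assumed values** (mean/SD in mg/dL, earlier then recent window).

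| Earlier | Recent | As written | 2-week CV | 4-week CV |
|---|---|---|---|---|
| 200/70 | 180/60 | 31.6% | 33.3% | 34.7% |
| 220/80 | 180/60 | 30.0% | 33.3% | 36.7% |
| 180/60 | 220/80 | 40.0% | 36.4% | 36.7% |
| 180/65 | 180/65 | 36.1% | 36.1% | 36.1% |

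In the first two rows the CV as written is below both proper CVs; in the third it is above both. With equal mean and SD in the two windows all three agree.

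**Step 5: partial wear.** Take 2880 readings per window, the minimum in Protocol 13.7, so 5760 in the period. The last 4032 are then 2880 recent and 1152 earlier readings. With 220/80 then 180/60, the CV as written is 34.4% against 36.7% from all 5760. With 4032 readings or fewer in the period, SD and mean use the same data and there is no mismatch.

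**The case against.** **The 4-week mean is an inference.** SAP 7.9.1.3.3 does not say that the mean covers 4 weeks; it points to a missing section. That stands as a limit. The certain defects are the dead reference and a cap on the SD that differs from the cap in the only control-group definition of the mean.

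**Period may mean a single 2-week window.** SAP 7.9.1.3.1 speaks of two periods of 2 weeks. On that reading the 8064 cap would never bind and nothing would be mismatched. The wording is loose, but this is the weaker reading: SAP 7.9.1.2 takes 8064 readings from each period, 7.9.1.3.2 allows 8064 per period, the lead-in to 7.9.1.3 combines the windows, and MAGE uses 4 weeks.

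**The treatment group.** A reader might infer the same fault there, a 6-month SD over a 4-week mean, by resolving the dead reference to the control-group section. The documents do not support this. SAP 7.9.2.3.2 defines the treatment group's own mean without a cap, 7.9.2.3.3 takes the SD without a cap, and 7.9.2.2 and 7.9.2.3.4 work from 6 months of data. Only the copied cross-reference is wrong.

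**Little depends on it.** This stands. SAP sections 4 and 6 call all analyses in the document exploratory, CV is not in the sequences of 7.5.1 and 7.5.2, and p-values for ancillary endpoints may not be claimed.

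**Conclusion.** Wrong as written, low severity. In the control group the SD and CV do not share a reading set with the mean for any subject with more than 4032 readings in a period, which is to be expected at good wear over two combined windows. This rests on taking 7.9.1.3.2 as the intended definition of the mean and on a period being the two windows combined.

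No single size can be given. In the three assumed cases with differing windows, the CV as written is 3.1 to 6.7 percentage points from the 4-week CV (34.7 − 31.6; 36.7 − 30.0). With equal SDs of 60 and means of 200 and 180, the gap is only 0.4 points (32.0 − 31.6).

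Two stronger statements are tempting and do not hold. A reader might infer that the relative error is simply the ratio of the window means, or that equal means remove it. In the example that ratio is 180/200 = 0.90, yet the error against the 4-week CV is about 1.4% or 9% depending on the earlier SD, and equal means with different SDs still leave an error. A reader might also infer that every control-group CV is affected; subjects with 4032 readings or fewer are not. No primary, secondary or safety result is touched.

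**What to change.** - **SAP 7.9.1.3.3:** replace 4032 by 8064, state that SD and mean come from the same readings, and point the mean to 7.9.1.3.2. This matches the window used in 7.9.1.2, the lead-in to 7.9.1.3, 7.9.1.3.2 and 7.9.1.3.4.
- **SAP 7.9.2.3.3:** correct the cross-reference to 7.9.2.3.2. Nothing else is needed there.

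The cost is a one-line text correction in each section. No new data are required, and neither the testing sequence nor the sample size changes.

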7.9.1.3.4 Amplitude of Glycemic Excursions (MAGE)

The excursion amplitudes of the glucose values measured by mean amplitude of glycemic excursions (MAGE) will be calculated for two periods using the blinded 4 weeks sensor glucose data from study phase and unblinded 4 weeks sensor glucose data from continuation phase. Analysis will be performed and reported.

7.9.1.3.5 Percentage of Time Spent in Auto Mode and in Manual Mode

The percentage of time spent in auto mode and manual mode for subjects in the continuation phase will be calculated as:

$$\frac{\text{time spent in auto/manual mode}}{\text{total time in AHCL therapy}} \times 100\%$$

Descriptive statistics for the percentage of time in auto mode and manual mode.

7.9.1.3.6 Percentage of Sensor Use for Continuation Phase

Descriptive statistics for the percentage of sensor use during the 6 months (After visit 9 to visit 13) continuation phase will be reported.

7.9.1.3.7 Change in Weight and BMI

The change in weight and BMI from 6 month (Visit 8) to end of 12 months continuation phase (Visit 13) will be calculated, analyzed and reported.

7.9.1.3.8 Change in Total Daily Insulin Dose

The change in total daily insulin dose from end of study phase to end of continuation phase will be computed, analyzed and reported. The total daily insulin dose will be based on self-reported data (from CRF) when in study period and will be based on pump data uploaded in CareLink Clinical in continuation phase. No comparison but only descriptive of TDD will be performed in the control phase.

7.9.1.3.9 Mean number of SMBG

The mean number of self-monitored blood glucose (SMBG) readings and mean of SMBG values will be calculated in study period and continuation phase from the pump data uploaded in CareLink Clinical and will be reported using summary statistics for quantitative variables.

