9.2. STUDY START and RUN-IN PHASE

Visit 1: Screening

At this visit, the subject will come at the site or the visit will be conducted remotely:

Medtronic Business Restricted

The Investigational site staff will:

- Determine if subject meets eligibility criteria (see sections 8.3 and 8.4).
- Collect demographic information (age, gender)
- Review subject's Medical History: including date of Type 1 DM diagnosis, indication for Glucose Monitoring System, diabetes-related complications, length of time on MDI therapy (inclusion criteria ≥ 2 years), mean daily insulin dose, insulin molecule, type of FGM or RT-CGM therapy (model) with average number of scans and percentage of sensor readings for FGM users over the previous month (based on downloaded report) or percentage of use of CGM over the previous month (based on downloaded report) for CGM users (*Download Reports will be printed, signed and filed in the source document of the subject*).
- Measure/Collect height and weight
- Perform blood sample collection for **HbA1c** with central laboratory kit.
 - *Reminder: HbA1c value $\geq 8.0\%$ (64 mmol/mol) for inclusion*
Screening status will be confirmed once HbA1c result is received by the site from central lab. Repeated testing will not be permitted. Lab result will be printed, signed and filed in the source document of the subject.

If the Visit 1 is conducted remotely, a nurse will visit the subject to collect the blood sample.

- Perform blood sample collection for **creatinine clearance** at local lab, if needed.
 - If creatinine clearance test was performed ≤ 12 months prior to screening, only confirm date of collection at local lab and creatinine clearance value in medical chart.
Reminder: creatinine clearance threshold for exclusion < 30 mL/min and must be calculated with the Cockcroft or MDRD equations. The sites will follow routine practice for evaluation of the creatinine clearance. If the visit 1 is conducted remotely, a nurse visit can be organized with the subject to collect the blood sample.
- Perform **pregnancy test** at local lab (urinary or blood test), if applicable. The blood or urine sample will be collected and disposed according to the local Lab procedure.
If the Visit 1 is conducted remotely, a nurse will visit the subject to collect the blood sample.
Alternatively, a urinary pregnancy test can be shipped to the subject, if applicable. Result will be documented in medical chart.
- Report any Adverse Events, if applicable

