	
visit is conducted remotely, the site can call the subject and record in medical chart or the subject can share the report via email.
 
▪ (Re)train the subject on Blinded CGM usage (sensor insertion, transmitter use)▪ Advise subject to perform at least 4 fingerstick blood glucose measurements per day with the study meter▪ Provide Blinded CGM Diary to Subject▪ Dispense supplies to subject (indicative quantity for 3 weeks):
○ 1 CONTOUR NEXT LINK 2.4 meter (subject uses same meter as dispensed previously)○ 80 Strips○ 2 Transmitters (1 is back-up)○ 4 sensors (2 are back-up)○ Charger○ One-press Serter▪ If Visit 7B is planned to be conducted remotely, a shipping box with instructions for supplies return will be provided/shipped to the subject.

Visit 7B [Visit 7A + 14 days (Window + 7 days)]

Site staff will call the subject to:

- Ensure CareLink upload was done / Advise subject to perform weekly CareLink uploads
- Review AHCL therapy / Adjust settings
- Retrain subject on Pump/CGM as needed.
- Review adverse event or device deficiency, if any.

Visit 7B [Visit 7A + 14 days (Window + 7 days)]

This visit can be done remotely or onsite.

If the Visit 7B is conducted remotely, the subject will return the devices via post-mail/courier, using the provided shipping box. Upon receipt of the supplies at the site, site staff will conduct Visit 7B.

Site staff will:

- Collect/Receive from the subject:
 - 1 Blinded CGM Diary
 - 2 Guardian Link 3 Transmitters
 - CONTOUR NEXT LINK 2.4 meter
 - 1 Charger
 - One-press serter
 - Unused Sensors

Treatment Arm	Control Arm
	
▪ Upload data from the Meter in CareLink using correct Subject ID (327-XXX-XXX).▪ Upload data of Transmitter using the Download utility. Make sure to use correct file name (Subject ID_Visit7B_DATE). Refer to Blinded CGM Instructions for more details.▪ Record % of use of CGM and average number of scans and % sensor readings for FGM over the previous 2 weeks (based on downloaded and printed report). If the visit is conducted remotely, the site can call the subject and write in medical chart or subject can share the report via email.▪ Review therapy / Adjust settings

Treatment Arm	Control Arm

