
Treatment Arm	Control Arm
	
▪ Advise subject to perform at least 4 fingerstick blood glucose measurements per day with the study meter.▪ Provide Blinded CGM Diary to Subject▪ Dispense supplies to subject (indicative quantity for 3 weeks):
○ 1 CONTOUR NEXT LINK 2.4 (subject uses same meter as dispensed previously)○ 80 Strips○ 2 Guardian Link 3 Transmitters (1 is back-up)○ 4 sensors (2 are back-up)○ Charger○ One-press serter

Treatment Arm	Control Arm

Visit 9: End of Study Phase [Visit 8 + 14 days (Window + 7 days)]
 
Site staff will call the subject to:
 
▪ Ensure CareLink upload was done / Advise subject to perform weekly CareLink uploads▪ Review AHCL therapy / Adjust settings▪ Review adverse event or device deficiency, if any.▪ Plan the next visits until Visit 13.	
Visit 9: End of Study Phase / Pump Start [Visit 8 + 14 days (Window + 7 days)]
 
This visit can be done remotely or onsite.
 
If the Visit 9 is conducted remotely, the subject will return the devices dispensed at Visit 8 via post-mail/courier, using the provided shipping box. Upon receipt of the supplies at the site, site staff will conduct Visit 9.
 
▪ Collect/Receive from the subject:
○ 1 Blinded CGM Diary○ 2 Guardian Link 3 Transmitters○ 1 CONTOUR NEXT LINK 2.4 meter○ 1 Charger○ One-press serter○ Unused Sensors▪ Upload data from the Meter in CareLink using correct Subject ID (327-XXX-XXX).▪ Upload data of Transmitter using the Download utility. Make sure to use correct file name (Subject ID_Visit9_DATE). Refer to Blinded CGM Instructions for more details.▪ Record % of use of CGM and average number of scans and % sensor readings for FGM over the previous 2 weeks (based on downloaded and printed report). If the visit is conducted remotely, the site can call the subject and document this in medical chart or subject can share the report via email.▪ Review adverse event or device deficiency, if any.▪ Site staff will train subject on the AHCL insulin pump and subject starts using the insulin pump.▪ Set-up subject CareLink Account.▪ Train subject to perform weekly CareLink uploads.

Treatment Arm	Control Arm

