5.2 Randomization

If subjects meet the inclusion and exclusion criteria, as well as all the following criteria assessed at the end of the run-in period, they may continue to participate in the study phase:

1. Subject has worn the sensor with blinded transmitter during the run-in period adequately, per investigator judgment.
2. Subject has shown acceptable tolerance to sensor wear, per investigator judgment.
3. CareLink data shows subject performed ≥ 2 finger stick blood glucose measurements daily, as determined by CareLink data upload as the mean number of SMBG/day over the past 14 days.
4. Subject has shown compliance with study procedures, per investigator judgment.

Subjects in each cohort will be randomized into 2 arms at the end of the run-in phase:

Cohort A (confirmatory): Subjects on **MDI + FGM** will be randomized into:

- Treatment Arm: Start AHCL (and stop FGM at visit 6A)
- Control Arm: Continue MDI + FGM

Cohort B (exploratory): Subjects on **MDI + Real-Time CGM** will be randomized into:

- Treatment Arm: Start AHCL (and stop CGM at visit 6A)
- Control Arm: Continue MDI + CGM

Each cohort will have a separate randomization.

6. Determination of Sample Size

Subjects entered the continuation phase after completed the study period. All subjects with data in the continuation phase will be included in the analysis. No power analysis has been done for this exploratory phase of the study. All analysis in this document is exploratory.

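### The SAP takes control-group SMBG in the study period from pump data, but that arm has no pump until Visit 9; the study-meter uploads at Visits 7B and 9 should be named instead

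*SAP*

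**What the plan says.** SAP 7.9.1.3.9, in the control-group part of the plan, covers the mean number of SMBG readings and the mean SMBG value. Both "will be calculated in study period and continuation phase from the pump data uploaded in CareLink Clinical" and are reported with summary statistics. SAP 7.9.2.3.9, for the treatment group, has the same text.

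SAP 5.2 gives the control therapy in the study phase as "Control Arm: Continue MDI + FGM" in Cohort A and "Control Arm: Continue MDI + CGM" in Cohort B. In protocol 9.3 the control column for Visit 9 is where "Site staff will train subject on the AHCL insulin pump and subject starts using the insulin pump"; the subject's CareLink account is set up at the same visit.

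The protocol does collect control-arm fingersticks in the study phase, by another route. At Visits 7A and 8 the meter is issued with 80 strips, and staff are told to "Advise subject to perform at least 4 fingerstick blood glucose measurements per day with the study meter". At Visits 7B and 9 the meter comes back and staff are told to "Upload data from the Meter in CareLink using correct Subject ID (327-XXX-XXX").

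For total daily insulin dose (TDD), SAP 7.9.1.3.8 names a different source for this arm: "The total daily insulin dose will be based on self-reported data (from CRF) when in study period". Among the visit procedures, an insulin dose is named only in the Visit 1 history: "length of time on MDI therapy (inclusion criteria ≥ 2 years), mean daily insulin dose, insulin molecule".

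**The concern.** A programmer who follows SAP 7.9.1.3.9 literally gets no study-period value for any control subject. The alternative is to choose a source and a time window that the SAP does not specify. SAP 7.12 requires departures from the plan to be described and justified in the report, so a departure is certain unless the text is corrected.

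The choice of window also affects interpretation. Study-phase meter readings come from short periods in which frequent testing was advised. Continuation-phase pump data span about six months, in which the meter also serves to calibrate the sensor. A summary of the two side by side, without stating the windows, would mix measurement conditions, and a difference in count could reflect the instructions given rather than behaviour on the device.

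**Working it through.** **1. Can control-arm pump data exist before Visit 9?** Infusion sets dispensed by visit in protocol 9.3 and 9.4, checked against Table 3:

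- Control: Visit 9, 10; Visit 11A, 30; Visit 12, 30. Sum 10 + 30 + 30 = 70. Table 3 gives 70.
- Treatment: Visit 5A, 10; Visits 6A, 7A, 8 and 12, 30 each. Sum 10 + 4 × 30 = 130. Table 3 gives 130.

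The visit lists reproduce the table exactly. Control infusion sets before Visit 9: 0 of 70. The pump itself is dispensed to this arm at Visit 9 (or shipped just before it if the visit is remote). No study-period pump data can be expected for any control subject.

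**2. When are control-arm meter readings planned?** Strips dispensed by visit:

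- Control: Visit 2, 80; Visit 7A, 80; Visit 8, 80; Visit 9, 250; Visit 11A, 750; Visit 12, 750. Sum 1990. Table 3 gives 1990.
- Treatment: Visit 2, 80; Visit 5A, 250; Visits 6A, 7A, 8 and 12, 750 each. Sum 80 + 250 + 4 × 750 = 3330. Table 3 gives 3330.

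After randomization and before pump start, the control arm receives 80 + 80 = 160 of 1990 strips, all tied to the two blinded-CGM windows. The meter is collected at Visit 4, reissued at 7A, collected at 7B, reissued at 8 and collected at 9. Study-phase SMBG for this arm is therefore planned only for 7A to 7B and 8 to 9.

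**3. Coverage.** Target dates: Visit 5 is Visit 4 + 7 days, Visit 7A is 3 months later, Visit 8 is 3 months after that, and Visit 9 is Visit 8 + 14 days. With 1 month = 30.44 days (assumed):

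- Visit 4 to Visit 9: 7 + 6 × 30.44 + 14 = 203.6, about 204 days.
- Metered days: 2 × 14 = 28. Share: 28 / 204 = 14%.
- If both windows run to their +7-day limit: 2 × 21 = 42 metered days, and Visit 9 moves 7 days later, so 42 / 211 = 20%.

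**4. TDD.** No arithmetic applies. The control columns for Visits 5 to 9 in protocol 9.3, and Table 5, list no insulin-dose item. They list therapy review and, at 7A, 7B, 8 and 9, recording of FGM or CGM use. The CRF (protocol 17.4), the content of the blinded-CGM diary (9.8.4) and the full procedures table (17.8) are separate documents, so whether a dose is recorded at the end of the study phase cannot be settled here.

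**The case against.** The case for leaving this alone is that it is a slip of one word. The control text matches the treatment-group text, so it was probably carried over. The meter data already sit in CareLink, and a competent programmer would find them. The protocol's own SMBG endpoint (5.3.3) is limited to the AHCL arm, so deleting the study period from the control section would also cure the problem. The parameter is ancillary, and SAP section 4 calls every analysis in the document exploratory. All of this stands, and it sets the size of the point. It does not make the written rule executable.

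Three stronger readings are tempting, and the documents do not support them.

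- **Control-group SMBG cannot be derived at all.** It can, from the meter uploads. The source is wrong; the data are not missing.
- **The control arm's end-of-study-phase insulin dose is not collected.** SAP 7.9.1.3.8 names a CRF source, and the CRF, diary and full procedures table are not available to check. Silence in protocol section 9 proves little: lost work or school days are also an endpoint and are equally absent from the visit lists.
- **A between-arm TDD comparison at 6 months is lost.** This SAP covers the continuation phase and evaluates the two groups independently (7.2). It plans no such comparison.

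SAP 7.9.1.3.8 says that the TDD change will be analysed, and then restricts the analysis to description in a control phase that it does not define. A change can be computed and reported descriptively, so this calls for clarification and is not a contradiction that alters a result.

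**Conclusion.** SAP 7.9.1.3.9 is wrong as written for the control group in the study period: the named source is empty for all control subjects in both cohorts. An existing source, the meter uploads at Visits 7B and 9, covers about 28 of 204 days (14%, or up to about 20% if both windows run to their limit). The coverage figures assume target visit dates and 30.44-day months. The finding of no pump data assumes that devices are dispensed as scheduled.

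The impact is small. SMBG is an exploratory ancillary parameter reported with summary statistics only, outside the fixed testing sequence. No primary, secondary or safety conclusion depends on it.

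TDD remains a query. The protocol lists no collection point after Visit 1 for the self-reported control-arm dose, and the sponsor should confirm that one exists.

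**What to change.** **SAP 7.9.1.3.9 (control group):**

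- Name the study-meter uploads at Visits 7B and 9 as the study-period source, and pump data as the continuation-phase source.
- Define the study-period windows as Visit 7A to 7B and Visit 8 to 9, with counts expressed per day of window.
- State that at least four fingersticks a day were advised in those windows.
- Present continuation-phase SMBG for the two-week windows at 9 and 12 months, alongside any all-data summary. SAP 7.9.1.2 already uses these windows for sensor data.

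If the sponsor does not want a study-period value for this arm, removing the study period from the section is an acceptable alternative and agrees with the protocol endpoint.

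**Query on SAP 7.9.1.3.8:** confirm that the CRF or the blinded-CGM diary holds a self-reported dose at the end of the study phase, name the visit, and state plainly that the control-group TDD change is descriptive only. If no such dose exists, say which value is used and label it by its visit.

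**Cost:** SAP wording and one check against the CRF. No new visit, procedure or protocol amendment is needed for the SMBG correction.
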